5. GENERAL METHODOLOGY AND CONVENTIONS

The primary analysis will be conducted when at least 50 dosed participants have completed at least 15 months of follow up post PF-07055480 infusion. The primary analysis is focused on the efficacy and safety during the follow-up through data cutoff postinfusion. The associated efficacy endpoints and analysis methods are listed in the tables below. The final analysis will be conducted when all dosed participants have completed the entire study (i.e., 5 years in follow-up duration per participant) or discontinued prematurely from the study. The planned endpoints after the primary analysis are focused on extended efficacy and longer-term safety. As this is an open-label study, the sponsor may conduct reviews of the data during the course of the study for the purpose of safety assessments. There may be several periodic reviews of data between the primary analysis and the final analysis for the purpose of publications and regulatory updates, etc.

Category of Endpoint	Primary Analysis Endpoints And Statistical Analysis Methods
Primary	Total ABR (treated and untreated bleedings) from Week 12 [Day 78] through at least 15 months (up to data cutoff) postinfusion of PF-07055480 will be compared to preinfusion

Category of Endpoint	Primary Analysis Endpoints And Statistical Analysis Methods
	of PF-07055480 (under SOC FVIII prophylaxis replacement regimen). A repeated measures negative binomial regression model will be used to test NI with NI margin = 3 bleeds/year at the one-sided alpha level = 0.025. If noninferiority is demonstrated, further testing for superiority would be conducted.
Key secondary	
 FVIII activity level > 5% at 15 months postinfusion of PF-07055480. The percentage of participants will be compared to a null hypothesis of percentage $\leq 68\%$ using an exact binomial test at the one-sided alpha level = 0.025. Based on the interim data of the Phase 1b/2 Study, 80% of participants in Cohort 4 (Phase 3 study dose) had a FVIII activity level greater than 5% at 18 months postinfusion. The null hypothesis of percentage $\leq 68\%$ will be rejected if the observed percentage is greater than 80%. Treated ABR from Week 12 [Day 78] through at least 15 months (up to data cutoff) post PF07055480 infusion will be analyzed separately using the same method as applied to Total ABR.
Secondary	
The following secondary endpoints will be analyzed with one-sided test at the alpha level = 0.025 (except for the paired t-test with 2-sided alpha = 0.05) if listed in Table 8 for the gatekeeping process or summarized.
 
 FVIII activity level from Week 12 through 15 months (up to Week 67) postinfusion of PF-07055480 will be summarized with descriptive statistics. FVIII activity level will be summarized with descriptive statistics by visit. The number (%) of participants achieving specific FVIII activity thresholds (e.g., <1%, 1-5%, >5-<15%, 15-<40%, 40-<150%, >150%) at selected visits postinfusion will be reported. AIR (from Week 12 [Day 78] through at least 15 months [up to data cutoff] postinfusion of PF-07055480) will be compared to preinfusion of PF-07055480 (under SOC FVIII prophylaxis replacement regimen) using a paired t-test. Annualized FVIII consumption from Week 12 [Day 78] through at least 15 months (up to data cutoff) postinfusion of PF-07055480 will be compared to preinfusion of PF-07055480 (under SOC FVIII prophylaxis replacement regimen) using a paired t-test. Treated ABR by cause (spontaneous or traumatic) from Week 12 [Day 78] through at least 15 months (up to data cutoff) postinfusion of PF07055480 will be analyzed separately using the same method as applied to Total ABR. Treated ABR by location (in joints, in target joints, or in soft tissue) from Week 12 [Day 78] through at least 15 months (up to data cutoff) postinfusion of PF-07055480 will be analyzed using the same method as applied to Total ABR. Total ABR (treated and untreated) by cause and by location from Week 12 [Day 78] through at least 15 months (up to data cutoff) postinfusion of PF-07055480 will be analyzed using the same method as applied to Total ABR. The percentage of participants without bleeds (from Week 12 [Day 78] through at least 15 months [up to data cutoff] postinfusion of PF-07055480) will be summarized. HJHS by visit postinfusion of PF-07055480 will be compared to baseline using a paired t-test. PRO endpoints (Haem-A-Qol, HAL) by visit postinfusion of PF07055480 will be summarized and compared to baseline to assess the improvement from baseline if baseline is available.

Category of Endpoint	Primary Analysis Endpoints And Statistical Analysis Methods
Exploratory	Details are provided in later sections in this SAP.

Category of Endpoint	Primary Analysis / Final analysis Endpoints And Statistical Analysis Methods
Secondary (all final analysis endpoints are considered secondary in this study)	Analyses will be performed by yearly interval (Month 15, Years 2 through 5). Selected endpoints (as described in Section 6) will be also analyzed by cumulative follow-up interval.
Exploratory	Details of analyses for FVIII activity assays and other exploratory endpoints are described in later sections.

Category of Endpoint	Ultrasound Substudy
Exploratory	Joint images will be reviewed following the extended ultrasound scale with a final score combining soft tissue and osteochondral subscores and compared to screening (at Week 24 and Week 52 or EOS).

Category of Endpoint	Vector Shedding Substudy
Exploratory	A subset of participants (N=12) will have more extensive vector shedding analysis performed to further characterize the kinetics of vector shedding.

Category of Endpoint	Joint X-Ray Substudy
Exploratory	X-ray assessments will be performed to assess damage within joints as detectable at a radiologic level. X-rays will be acquired at Screening or not later than Week 4/Visit 6, Week 156, and Week 260 or Early Discontinuation Visit.

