9.4.1. Efficacy Analyses

The primary analysis is planned after at least 15 months of follow-up postinfusion in at least 50 dosed participants, with endpoints in the table below. The planned endpoints after the primary analysis, so called final analysis, are focused on extended efficacy and longer-term safety.

Category of Endpoint	Primary Analysis Statistical Analysis Methods
Primary	
 Total ABR (treated and untreated bleedings) from Week 12 through at least 15 months (up to data cutoff) postinfusion of PF-07055480 will be compared to preinfusion of PF-07055480 (under SOC FVIII prophylaxis replacement regimen). A repeated measure negative binomial regression model will be used to test NI with NI margin = 3 bleeds/year at one-sided alpha level = 0.025. If the noninferiority on Total ABR is established, subsequently testing for superiority will be conducted.
Key secondary	
 FVIII activity level $>5\%$ at 15 months postinfusion of PF-07055480. The percentage of participants will be compared to a null hypothesis of percentage $\leq 68\%$ using an exact binomial test at the one-sided alpha level = 0.025. Based on the interim data of the Phase 1/2 Study, 80% of participants in Cohort 4 (Phase 3 study dose) had a FVIII activity level greater than 5% at 18 months postinfusion. The null hypothesis of percentage $\leq 68\%$ is determined so it could be rejected when the observed percentage is greater than 80%. ABR from Week 12 through at least 15 months (up to data cutoff) postinfusion of PF-07055480 will be compared to preinfusion of PF-07055480 (under SOC FVIII prophylaxis replacement regimen) and analyzed separately using the same method applied to Total ABR.

Category of Endpoint	Primary Analysis Statistical Analysis Methods

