Any sample taken within 72 hours for standard half-life products or 120 hours for extended half-life products after administering exogenous FVIII replacement therapy for any purpose (including treatment of bleeding or prevention purposes) will be excluded. When multiple appropriate FVIII activity observations are collected on the same day for a participant, the average level of these observations will be used for the given day. Additionally, any FVIII activity levels after the resumption of FVIII prophylaxis regimen (if necessary) will be replaced with 0.9% for analysis purposes, and therefore considered as having FVIII activity \leq 5%. FVIII activity collected at unscheduled visits will be mapped to a visit if the data collection date falls into the protocol-defined visit window.

Participants who prematurely discontinue from the study prior to reaching Month 15 visit will be considered as having FVIII activity \leq 5% for the main analysis of this endpoint.

The FVIII activity level at 15 months post PF-07055480 infusion will include all appropriate FVIII activity data collected around the Week 65 visit (from Week 63 through Week 67), including unscheduled visit observations. In a case when multiple observations fall into the same visit window, an average FVIII activity level will be taken over these observations and included in the analysis.

For participants who have not discontinued from the study before Week 65 visit and have not resumed prophylaxis, if there are no appropriate FVIII activity levels for a participant in the main analysis population during the visit window of Week 65 visit (from Week 63 through

Week 67), the missing FVIII activity level will be imputed with the earliest appropriate FVIII activity level collected post Week 65 visit window. In case there are no appropriate FVIII activity levels post Week 65 visit window, the FVIII activity at Week 65 will be considered as missing and excluded from the assessment.

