4. ANALYSIS SETS (POPULATIONS FOR ANALYSIS)

For purposes of analysis, the following populations are defined:

Population	Description	Applicable Analysis (for additional information refer to Section 6)
Enrolled	All participants who sign the informed consent form (ICF) and meet all inclusion/exclusion criteria.	Disposition events summary
Dosed/Safety	All participants enrolled in the study and who receive the study intervention.	Demographic and baseline characteristics, hemophilia history, medical history, safety, nAbs, ADA, FVIII antigen, von Willebrand factor, vector shedding assessments, joint health assessments, efficacy sensitivity/supplementary analyses, PRO analyses, and coagulation activation tests.
Evaluable	
All participants enrolled in the study and who receive the study intervention and have no significant interruption of efficacy measurement.
 
The ‘Evaluable’ analysis population will include participants who receive the study intervention (full dose of infusion) and exclude participants with significant interruption of efficacy measurement. The significant interruption would occur if the participant discontinues from the study, is lost to follow-up, has significant
	Efficacy sensitivity/supplementary analyses

Population	Description	Applicable Analysis (for additional information refer to Section 6)
	interruption in data collection, or has a major protocol deviation.	
Efficacy	All participants in the 'Dosed' population who have completed at least 6 months of follow up in the lead-in study and at least 15 months of follow up or discontinued from the study C3731003 prior to the data cutoff for reporting.	Main analysis population for efficacy
Ultrasound Substudy	All participants who sign the additional ICF for the ultrasound substudy and meet all inclusion/exclusion criteria, and the participant's joint ultrasound have been reviewed following the extended ultrasound scale at baseline, and any data post-baseline.	HEAD-US ultrasound scale - total score and subscores, demographic and baseline characteristics, AEs, disposition, and FVIII activity level data.
Vector Shedding Substudy	All participants who sign the additional ICF for the Vector Shedding substudy and meet all inclusion/exclusion criteria, and who provide any additional vector shedding data for analysis.	Shedding vector levels in PBMC, saliva, urine, semen, and plasma; demographic and baseline characteristics, AEs, disposition, and FVIII activity level data.

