5.1. Hypotheses and Decision Rules

In this study, all hypothesis testing will be one-sided with Type I error of 0.025.

The primary objective is to evaluate the efficacy of a single infusion of PF-07055480 in participants ≥ 18 and < 65 years of age with moderately severe to severe hemophilia A (FVIII:C $\leq 1\%$).

For the primary efficacy analysis, the hypothesis testing written in statistical notation is:

H_0 : Total ABR_{PF-07055480} – Total ABR_{FVIII prophylaxis} ≥ 3.0 versus H_a : Total ABR_{PF-07055480} – Total ABR_{FVIII prophylaxis} < 3.0

where Total ABR_{PF-07055480} represents the mean Total ABR post PF-07055480 infusion, while Total ABR_{FVIII prophylaxis} represents the mean Total ABR on prior routine prophylaxis FVIII replacement. The proposed non-inferiority margin is 3.0 bleeds/year.

If the upper bound of the confidence interval of the difference (Total ABR_{PF-07055480} – Total ABR_{FVIII prophylaxis}) is less than 3.0, the noninferiority would be demonstrated.

For the key secondary endpoint (FVIII activity level $> 5\%$), the percentage of participants with FVIII activity level at 15 months post PF-07055480 infusion will be compared to the null hypothesis of percentage $\leq 68\%$ using an exact test for binomial proportion. The other key secondary endpoint (Treated ABR) will be tested for noninferiority using the same method and margin as described above for the Total ABR.

A gatekeeping process will be applied to control for multiple endpoint comparisons at the primary analysis. The subsequent hypothesis testing will only be performed after success on the previous hypothesis test. The testing ceases when a failure occurs. The sequence of gatekeeping process is displayed in Table 8 below. Note that only selected endpoints are included in the sequence.

Table 8. Gatekeeping Sequence

Order in the testing sequence	Statistical testing
1	Non-inferiority in Total ABR from Week 12 [Day 78] through at least 15 months (up to data cutoff) postinfusion compared to prior prophylaxis treatment with a NI margin of 3
2	Percentage of participants with FVIII activity $> 5\%$ at 15 months postinfusion compared to the null hypothesis of percentage $\leq 68\%$
3	NI in Treated ABR from Week 12 [Day 78] through at least 15 months (up to data cutoff) postinfusion compared to prior prophylaxis treatment with a NI margin of 3

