6.2. Secondary Endpoints

6.2.1. Key Secondary Endpoint: FVIII Activity Level > 5%

6.2.1.1. Main Analysis

The percentage of participants with FVIII activity level > 5% at 15 months postinfusion will be tested against the null hypothesis of percentage $\leq 68\%$ using a one-sided exact binomial proportion test at one-sided alpha = 0.025 using the ‘Efficacy’ population. The number of participants in the analysis population, number of participants with FVIII activity level > 5%, percentage with the 95% CI of the percentage, and p-value will be provided.

Participants who prematurely discontinue from the study or resume prophylaxis regimen prior to reaching Month 15 visit will be considered as having FVIII activity $\leq 5\%$ for this percentage assessment.

The 15 months postinfusion is corresponding to a study visit at Week 65. Any appropriate FVIII activity data collected at unscheduled visits during Week 63 to Week 67 (i.e., the visit window for Week 65 visit) will be included in this assessment. Imputation rules as described in [Section 3.2.1](#) will be applied.

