Total ABR postinfusion (from Week 12 through at least 15 months [up to data cutoff] postinfusion of PF-07055480) with imputation	US-specific analysis: supplementary	Efficacy	Same as for the main analysis and the imputation rules described in Table 10 will be applied.	Same as for the main analysis with hypothesis testing.
Assessment of treatment failure	Primary analysis: supplementary analysis	Dosed	Details are described in Section 6.1.1.3.	Participant-level data listing.
FVIII activity level > 5% at 15 months postinfusion of PF-07055480	Primary analysis: main analysis	Efficacy	
 Any sample taken within 72 hours after administering standard half-life exogenous FVIII replacement therapy, or 120 hours for products with extended half-life, for any purpose (including treatment of bleeding or prevention purposes) will be excluded. Participants who resume prophylaxis regimen prior to reaching Month 15 visit will be considered as having FVIII activity level $\leq 5\%$. Participants who discontinue from the study prior to reaching Month 15 visit will be considered as having FVIII activity level $\leq 5\%$. Missing FVIII activity level will be imputed with the earliest FVIII level collected post Week 65 (Month 15) visit 	Exact test for binomial proportion

Endpoint	Analysis Type	Population	Data Inclusion and Rules for Handling Intercurrent Events and Missing Data	Analysis
			window. In case there are no FVIII activity levels collected post Week 65 visit window but the participant has not discontinued from the study, the FVIII activity level will be considered as missing and excluded from the analysis.	
FVIII activity level <1%, 1-5%, >5-<15%, 15-<40%, 40-<150%, >150% at Week 12, Week 26 (Month 6), Week 52 (Month 12), Month 15, Month 18, Year 2, Year 3 postinfusion	Primary analysis: sensitivity analysis	Dosed	See imputation rules described in Section 3.2.5 .	Number (%) of participants
Treated ABR (from Week 12 through at least 15 months [up to data cutoff] postinfusion of PF-07055480)	Primary analysis: main analysis	Efficacy	
 Any data after the resumption of FVIII prophylaxis regimen (if necessary) will be excluded. Data after study discontinuation will not be imputed. 	Same as above for Total ABR from Week 12 through at least 15 months (up to data cutoff).

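### SAP Section 5 says an observed rate above 80% always rejects the 68% null; under the SAP's own exact test this fails at 41/51, 42/52 and 45/56

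*SAP*

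**What the plan says.** The key-secondary row of the analysis table in SAP Section 5 specifies an exact binomial test against a null of at most 68% at one-sided alpha 0.025. It reports that 80% of Phase 1b/2 Cohort 4 exceeded 5% activity at 18 months. It then states that the 68% null "will be rejected if the observed percentage is greater than 80" percent. No sample size is attached.

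Protocol 9.4.1 uses the same figure more cautiously, as the reason for choosing 68%: the null value "is determined so it could be rejected when the observed percentage is greater than 80" percent.

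Elsewhere the SAP gives only the test. Section 5.1 states: "In this study, all hypothesis testing will be one-sided with Type I error of 0.025". Section 6.2.1.1 tests the percentage "using a one-sided exact binomial proportion test at one-sided alpha = 0.025". Appendix 2 lists "Exact test for binomial proportion". None of these mentions 80%.

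Three passages determine the denominator:

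- SAP Section 5 triggers the analysis "when at least 50 dosed participants have completed at least 15 months of follow up".
- SAP Section 4 limits the Efficacy population to dosed participants whose lead-in lasted 6 months or more. For the period after infusion it takes those with "at least 15 months of follow up or discontinued from the study C3731003 prior to the data cutoff for reporting".
- SAP 3.2.1 scores discontinuation or resumed prophylaxis before Month 15 as activity of 5% or less, so those participants stay in the denominator. If a participant still in the study and off prophylaxis has no usable value in or after the Week 65 window, "the FVIII activity at Week 65 will be considered as missing and excluded from the assessment".

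**The concern.** An exact binomial test has a critical count that depends on n, so a fixed percentage cannot serve as its rejection boundary at every n. The SAP states one without a condition, in the same table entry as the exact test. Where the two disagree, this sentence says the null is rejected while the exact p-value exceeds 0.025 and the exact 95% confidence interval includes 68%.

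The endpoint is step 2 of nine in Table 8, and testing stops at the first failure. Steps 3 to 9 (treated ABR noninferiority, the superiority tests and the two PRO scores) all depend on it. A plan should not contain a sentence that could be cited for a different answer at a borderline count, least of all in an open-label study.

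**Working it through.** **Inputs**

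- Null proportion 0.68, exact binomial test, one-sided alpha 0.025 (SAP Section 5 and 6.2.1.1).
- Stated threshold: observed percentage above 80% (SAP Section 5).
- Range of n: 50 (minimum number of completers) to 70 (approximate enrolment, SAP 2.3).

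**Formulas**

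- Exact p-value for x responders: p = P(X ≥ x | n, 0.68) = Σ C(n,k) · 0.68^k · 0.32^(n−k), summed over k = x to n.
- Exact critical count x_c: the smallest x with p ≤ 0.025.
- Stated-rule count x_80: the smallest x with x/n > 0.80, that is 5x > 4n.
- The sentence is false at any n where x_80 < x_c.

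**Reproducing the 80% figure at n=50**

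- 40/50 = 80.0%: p = 0.0437, not rejected.
- 41/50 = 82.0%: p = 0.0206, rejected.

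Above 80% is therefore exactly the boundary at n=50.

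**Where the sentence fails, n=50 to 70**

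| n | 0.8n | x_80 | Observed | Exact p at x_80 | Exact 95% CI | x_c |
|---|---|---|---|---|---|---|
| 51 | 40.8 | 41 | 80.4% | 0.0363 | 66.9% to 90.2% | 42 (82.4%, p=0.0167) |
| 52 | 41.6 | 42 | 80.8% | 0.0300 | 67.5% to 90.4% | 43 (82.7%, p=0.0136) |
| 56 | 44.8 | 45 | 80.4% | 0.0292 | 67.6% to 89.8% | 46 (82.1%, p=0.0136) |

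These are all the failures in the range, with one count at each size. At the other 21 − 3 = 18 sizes, any percentage above 80% does reject.

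**Where the exact test also rejects at or below 80%**

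- 52/65 = 80.0%, p = 0.0228.
- 55/69 = 79.7%, p = 0.0221.
- 56/70 = 80.0%, p = 0.0185.

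These do not contradict the sentence, which gives a sufficient condition only. They do show that 80% is not the critical value at those sizes. The two boundaries coincide at 18 − 3 = 15 sizes: n = 50, 53–55, 57–64 and 66–68.

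**How easily a failing size arises**

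Suppose 41 of 50 completers exceed 5% and one participant discontinued before Month 15. The result is 41/51 = 80.4%. Without the discontinuation, 41/50 rejects (p = 0.0206). With it, the observed rate is still above 80% but the test does not reject (p = 0.0363). Two discontinuations on top of 50 completers give n=52.

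**Dependence on the test**

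An uncorrected normal approximation would reject at 42/52 (p = 0.0242) and 45/56 (p = 0.0237) but not at 41/51 (p = 0.0289). Mid-p gives the same pattern (0.0218, 0.0214 and 0.0265). With a continuity correction none of the three rejects. The SAP names the exact test, so the table above applies.

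**The case against.** The strongest reply is that the sentence is not a decision rule. It closes a short rationale that runs from the Phase 1b/2 result to the choice of 68%, and the protocol gives the same rationale in softer terms. The decision rules are in SAP 5.1 and Table 8, which do not mention 80%. SAP 2.1 declares no modification of the protocol's analysis plan. The figure is exact at n=50 and the sentence holds at 18 of 21 sizes, so what is missing is a qualifier. At a contested count the planned output (percentage, confidence interval and p-value) would itself show non-rejection.

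Most of this stands. The exact test governs, and the sentence changes no planned result. If 80% were used literally as the rule, its one-sided size would be 3.6%, 3.0% and 2.9% at n=51, 52 and 56. No other part of the SAP uses it that way, so these figures are not error inflation in the plan.

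The reply does not make the sentence true. The SAP moved from saying the null could be rejected to saying it will be, dropped any reference to n, and left the statement beside a test that contradicts it at sizes the plan allows.

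**Conclusion.** The concern holds and is minor. The unconditional statement in SAP Section 5 is wrong at 41/51, 42/52 and 45/56, and only there for n from 50 to 70. It does not put the gatekeeping result in doubt, because the exact test is the only procedure named where the decision and analysis are specified.

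This rests on the SAP's stated test, null and alpha, and on a denominator between 50 and about 70. The sentence would also fail at n=45 to 49 (for example 40/49 = 81.6%, p = 0.0252). Reaching those sizes is unlikely, because it needs several participants who are still in the study, off prophylaxis and without any usable value in or after Weeks 63 to 67.

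**What to change.** Delete the 80% sentence from SAP Section 5. Alternatively, replace it with: *The null hypothesis is rejected if the exact one-sided p-value is at most 0.025 for the actual denominator (for example, at least 41/50, 42/51, 43/52, 46/56, 49/60, 52/65 or 56/70).* The list of counts is optional.

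Protocol 9.4.1 can stay as it is, since it gives the figure only as the reason for choosing 68%.

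The cost is one sentence in the SAP. The test, alpha, null value, sample size and testing order do not change.
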